13. STATISTICAL CONSIDERATIONS

A statistical analysis plan (SAP) will be produced prior to the database lock and analysis of the study. Any deviations from the original SAP will be described in the final clinical study report.

13.1 Sample Size, Power and Significance Levels

A total of 20 patients will be enrolled in this study. There is no formal sample size: Calculation and analysis is descriptive only.

13.2 Interim Analysis

An interim analysis will be conducted at the end of the Single Blind phase of the study and may also be considered during the OLE phase, if long term data is required to support New Drug Application/Marketing Authorization Application submissions.

13.3 Analysis Sets

13.3.1 Safety Set

All subjects who are treated and receive at least one dose of IMP will be included.

The Safety set is the primary analysis set for all safety endpoints.

13.3.2 Pharmacokinetic Analysis Set

All subjects who are treated and receive at least one dose of IMP and who provide some on-treatment data will be included.

The PK analysis set is the primary analysis set for all PK endpoints.

13.3.3 Protocol Deviations

Any protocol deviations will be listed and reasons for exclusion from the analysis populations will be summarized

13.4 General Considerations

Unless stated otherwise, continuous variables will be summarized showing the number of non-missing values (n), mean, standard deviation, median, minimum and maximum and categorical variables will be summarized showing the number and percentage of patients falling in each category. Summaries will be presented for data recorded pre-treatment, during each 25 day dosing phase (placebo and CBD) and during the OLE phase separately.

13.5 Accountability and Background Characteristics

13.5.1 Enrolment and Disposition

All patients (screened, treated, completing the study and those prematurely terminated IMP) will be accounted for in the enrolment and disposition summary tables.

13.5.2 Baseline and Demographic Characteristics

Age, sex, race (as allowed per local regulations) and any other demographic or baseline characteristics will be summarized, using appropriate summary statistics.

13.5.3 Medical History

Previous and current medical conditions will be summarized by system organ class, including details of the duration of epilepsy and the types of seizures currently experienced by the patients.

13.5.4 Concomitant Medication

Concomitant medications taken prior to and during the study will be summarized, by medication class and active ingredients. Summaries of medications taken during the IMP treatment phases and during OLE will be presented separately.

13.6 Endpoints and Statistical Methods

13.6.1 Primary Endpoint(s)

The primary endpoints of the study are the pharmacokinetic parameters (C_{max} , t_{max} , $AUC_{(0-\infty)}$, $AUC_{(0-t)}$, $t_{1/2}$) of the following analytes:

- CLB
- N-desmethylclobazam (N-CLB)
- CBD
- CBD major metabolites

13.6.2 Secondary Endpoint(s)

The secondary endpoints of the study are the safety parameters (see [Section 13.6.5](#)).

13.6.3 Pharmacokinetics

Calculation of PK parameters will be based on actual blood sampling times [h] (relative to the corresponding administration time) rounded to two decimal digits with negative pre-dose times set to zero. Plasma concentrations of CLB, N-CLB, CBD and

the major metabolites will be displayed graphically, summarized and listed. For descriptive statistics, values below the lower limit of quantification of the assay (LLOQ) will be excluded from any calculations. Descriptive statistics of concentrations will be calculated if at least half of the individual data points that have been measured are equal to or above the LLOQ.

For calculation of the PK parameters, the following rules will be applied:

At time zero and at time points in the lag-time between time zero and the first quantifiable concentration, concentrations below the LLOQ will be set to zero. All other concentrations below the LLOQ will not be used in calculations.

Variables derived from plasma concentrations:

- Concentration maximum (C_{\max}): Highest observed plasma concentration of the measured concentration-time profile. Dimension: [amount / volume].
- Terminal half-life $t_{1/2} = \ln(2)/\lambda_z$.
- The rate constant of the terminal phase λ_z will be determined by linear regression of log-transformed concentration data after the time of maximum concentration. A sequence of terminal elimination rate constants will be created by linear regression. Linear regressions are repeated using the last three points with a quantifiable concentration, the last four points, the last five points etc. For each regression, an adjusted R^2 is computed. The regression with the largest adjusted R^2 is selected to estimate the terminal half-life. Dimension: [time].
- Area under the concentration-time curve from administration until the last sampling point (t) equal or above the LLOQ $AUC_{(0-t)}$ will be calculated by the linear trapezoidal formula. Dimension: [time • amount / volume].
- Area under the concentration-time curve extrapolated to infinity: $AUC_{(0-\infty)} = AUC_{(0-t)} + C_{\text{last}}/\lambda_z$ and C_{last} is the concentration observed at the last time point with a quantifiable concentration, λ_z refers to the terminal elimination rate constant. Dimension: [time • amount / volume].
- Time of maximum concentrations: T_{\max} will be taken as the time after administration at which C_{\max} occurs. Dimension: [time].
- PK parameters for each analyte will be summarized for the two treatment phases of the study separately, as appropriate.
- In order to assess whether the presence of CBD alters the PK profile of CLB (or N-CLB), a standard 90% confidence interval (CI) approach for the between group ratios of geometric means of C_{\max} , $AUC_{(0-t)}$, and $AUC_{(0-\infty)}$ will be carried on logarithm scale using a linear mixed effect model with treatment (CBD or placebo) as fix effect and subject as a random effect. The no-effect boundary will be set between 0.5 and 2.0 and if the 90% CI for the ratio of the geometric means of a PK variable falls within the interval [0.5, 2.0], a lack of meaningful effect will be declared.

13.6.4 Safety

13.6.4.1 Treatment Compliance and Extent of Treatment Exposure

Treatment compliance and exposure to treatment will be summarized for each phase of the study separately.

13.6.4.2 Adverse Events

AEs will be coded according to the Medical Dictionary for Regulatory Activities dictionary.

A treatment emergent AE is one that started, or worsened in severity or seriousness, following the first dose of IMP.

Descriptive presentations of treatment emergent AEs will be given by preferred term and system organ class for the safety analysis set. The number of patients reporting at least one AE will be provided. Summaries will be provided for each phase of the study separately.

The following summaries will be produced:

- All-causality AEs.
- Treatment related AEs.
- All-causality AEs by severity.
- All-causality serious AEs.
- Treatment related serious AEs.
- AEs reported as leading to permanent cessation of study treatment.
- Fatal AEs.

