12.5 Causality Assessment

Causality assessment is required for all AEs and SAEs. Causality assessment must only be assigned by the investigator. All cases judged as having a reasonable suspected causal relationship to the study medication must be reported as such. The expression "*reasonable causal relationship*" is meant to convey in general that there are facts (evidence) or arguments to suggest a causal relationship.

The following question which must be answered by the investigator for all AEs is used to capture the reasonable causal relationship of an event to the study medication:

"In your opinion is there a plausible relationship to the study medication?" The answer is "yes" or "no".

Events that start before the first dose of study medication (pre-treatment) should be considered as not causally related. Where a pre-treatment event worsens in severity following the first dose of study medication, a new event record should be entered into the CRF.

Considering the explanation given above, investigators are strongly encouraged to express their opinion on what the cause of an AE might be. For individual patients, the investigator is usually in the best position to assess the underlying suspected cause of an AE. For all AEs and especially SAEs, it is important that the investigator assess not only the possible role of the study medication but also competing etiological factors as the underlying cause. Factors for consideration may include:

- Medical history.
- Lack of efficacy/worsening of treated condition.
- Concomitant or previous treatment.
- Withdrawal of study medication.
- Protocol-related procedure.

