12.3 Reporting Procedures for Serious Adverse Events

All SAEs occurring during the study must be reported to GW with any other supporting information and recorded in the AE section of the CRF. Any on-going

SAEs should be followed up until resolution wherever possible. For all deaths, the working diagnosis or cause of death as stated on a death certificate, available autopsy reports and relevant medical reports should be sent to GW promptly.

All SAEs must be reported directly to GW PVD within 24 hours of discovery or notification of the event. All SAE information must be recorded on the SAE forms provided in the site files and faxed to GW PVD. Additional information received for a case (follow-up or corrections to the original case) need to be detailed on a new SAE form, signed/dated and faxed to the GW PVD and the AE section of the CRF must be updated.

The investigator should continue to document all AEs which occur up to the last formal follow-up visit (Visit 13 for patients entering the OLE and Visit 6 for those patients that are not entering the OLE). If the investigator subsequently becomes aware of any deaths or a new IMP-related SAE after the last formal follow-up period of the study, these should still be reported to the GW PVD.

Any other problem discovered outside these time limits which is deemed to be an unexpected safety issue and is likely to have an impact on patients who have participated in the study, then these should be treated as an SAE and reported to GW PVD. Such post study SAEs do not need to be recorded on the patient's CRF if editing rights to the CRF have been removed.

Contact details for the GW PVD are provided at the front of the site files for all study centers, and upon the GW SAE Report form.

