12.5 Causality Assessment

Causality assessment is required for all AEs and SAEs. Causality assessment must only be assigned by the investigator. All cases judged as having a reasonable suspected causal relationship to the study medication must be reported as such. The

expression “*reasonable causal relationship*” is meant to convey in general that there are facts (evidence) or arguments to suggest a causal relationship.

The following question which must be answered by the investigator for all AEs is used to capture the reasonable causal relationship of an event to the study medication:

“In your opinion is there a plausible relationship to the study medication?” The answer is “yes” or “no”.

Events that start before the first dose of study medication (pre-treatment) should be considered as not causally related. Where a pre-treatment event worsens in severity following the first dose of study medication, a new event record should be entered into the CRF.

Considering the explanation given above, investigators are strongly encouraged to express their opinion on what the cause of an AE might be. For individual patients, the investigator is usually in the best position to assess the underlying suspected cause of an AE. For all AEs and especially SAEs, it is important that the investigator assess not only the possible role of the study medication but also competing etiological factors as the underlying cause. Factors for consideration may include:

- Medical history.
- Lack of efficacy/worsening of treated condition.
- Concomitant or previous treatment.
- Withdrawal of study medication.
- Protocol-related procedure.

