12.6 Reporting Procedures for All Adverse Events

All AEs* (including SAEs) occurring during the study will be reported on the running logs in the AE section of the CRF. This includes all events from the time following screening (Visit 1) to post study follow-up (Visit 13 for patients entering the OLE and Visit 6 for those patients that are not entering the OLE), whether or not attributed to IMP and observed by the investigator or patient.

*For the patient’s expected seizure types, these do not routinely require documentation as AEs. However, any worsening, including change in the pattern or severity of seizures must be documented as an AE. Any AE which meets SAE criteria should still be reported as a SAE.

The following information will need to be provided for all AEs:

A) Adverse Event (Diagnosis or Syndrome if known, or Signs and Symptoms)

Where the investigator cannot determine a diagnosis, signs or symptoms should be recorded on the AE section of the CRF. Once a diagnosis has been determined the AE section of CRF must be updated to reflect the diagnosis in replacement of the original symptoms. In circumstances where only a provisional diagnosis is possible (working diagnosis), the CRF must be updated to reflect the provisional diagnosis in replacement of the original symptoms. In some circumstances it may be relevant for the investigator to include the symptoms alongside the diagnosis in the verbatim event description. However, the diagnosis (full or provisional) should be clearly stated e.g., fever and malaise due to a respiratory tract infection.

B) Adverse Event Start Date and Stop Date

The start and stop dates of the event must be provided. All AEs require these fields to be completed in full. Partial dates or missing dates are not normally acceptable and significant effort must be undertaken to obtain any unknown information. If a precise date is not known an estimated date should be provided instead. When a complete date cannot be given then record as much information as possible (i.e., month and year or in exceptional circumstances just year). When the actual start date becomes known the CRF must be updated to replace the previously recorded date.

C) Outcome

The outcome of the event must be recorded accurately and classified into one for the following categories:

- Recovered.
- Recovered with sequelae.
- Continuing.
- Patient died.

D) Severity

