When describing the severity of an AE the terms mild, moderate, or severe should be used. Clinical judgment should be used when determining which severity applies to any AE.

If the severity of an AE fluctuates day-to-day, for example, a headache or constipation, the change in severity should not be recorded each time, instead only the worst observed severity should be recorded with AE start and stop dates relating to the overall event duration regardless of severity.

A severe AE is not the same as a SAE. For example, a patient may have severe vomiting but the event does not result in any of the SAE criteria above. Therefore it should not be classed as serious.

E) Causality

See [Section 12.5](#) above.

F) Action Taken with Study Medication

This question refers to the action taken with the IMP due to an AE. The action with the IMP must be classed as:

- None.
- Dose reduced temporarily.
- Dose reduced.
- Study medication interrupted.
- Study medication stopped.

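### Section 12.5 opens a new record for a pre-treatment AE only when its severity worsens, so one that only turns serious on treatment is kept out of the treatment-related tables

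*Protocol*

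**What the plan says.** Section 13.6.4.2 defines the events to be tabulated: "A treatment emergent AE is one that started, or worsened in severity or seriousness, following the first dose of IMP". An event already present before dosing can therefore become treatment-emergent in two ways, through severity or through seriousness. The planned summaries include treatment-related AEs, all-causality serious AEs and treatment-related serious AEs.

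Section 12.5 sets causality and recording for the same events. On causality: "Events that start before the first dose of study medication (pre-treatment) should be considered as not causally related". On recording: "Where a pre-treatment event worsens in severity following the first dose of study medication, a new event record should be entered into the CRF". Seriousness is not mentioned as a reason for a new record.

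Section 12.6 separates the two attributes: "A severe AE is not the same as a SAE". It also provides: "Any AE which meets SAE criteria should still be reported as a SAE". Section 12.3 adds: "All SAEs occurring during the study must be reported to GW with any other supporting information and recorded in the AE section of the CRF". When follow-up information arrives on an SAE, a new SAE form is completed and "the AE section of the CRF must be updated".

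The wording of 12.5 is the same in Protocol Versions 1 and 2. The Version 2 text at hand stops at 13.5.3, so 13.6.4.2 is read from Version 1. The change table of Amendment 1 lists no change to 13.6.4.2 or to 12.5.

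**The concern.** The analysis definition has two triggers for a pre-existing event and the recording rule has one. An event can turn serious, for instance by requiring hospitalization, while its grade on the mild, moderate and severe scale stays the same. Under 12.5 nothing then requires a second record. The only record has a pre-dose start date and falls under the instruction to regard it as unrelated, although the change that made it serious took place on study drug.

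The treatment-related summaries are at stake. A related or unrelated entry fixed by onset date, and not by a judgement on the deterioration, can only move events out of those tables, never in. A statistical analysis plan can define how a flag is derived, but it cannot supply an investigator's causality answer that the protocol told the site to pre-set.

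**Working it through.** No sample size, power or event count is involved, and the plan gives no figure to reproduce. The check traces cases through the rules.

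Common inputs: onset after Visit 1 and before the first dose of GWP42003-P or placebo; the event becomes serious after that dose.

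| Step | Case A: severity also worsens | Case B: severity unchanged |
|---|---|---|
| New record under 12.5 | Yes | Not called for |
| Start date available | Post-dose, on the new record | Pre-dose, on the only record |
| Causality under 12.5 | Assessed afresh on the new record | Unrelated by rule |
| Reported as an SAE and entered in the CRF (12.3, 12.6) | Yes | Yes |
| Treatment-emergent under 13.6.4.2 | Yes | Yes, through seriousness |
| All-causality serious AEs | Included | Included by definition, but missed by a flag that uses only the start date |
| Treatment-related AEs and treatment-related serious AEs | Included if judged related | Excluded whatever the investigator thinks of the deterioration |

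1. Cases A and B differ only in whether the severity grade moved. Section 12.6 treats severity and seriousness as different attributes, so Case B can occur.

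2. In Case B the two sections conflict. Section 13.6.4.2 treats the post-dose change as a treatment-period event, while 12.5 fixes its causality from the date the original event began.

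3. Scale: 20 patients randomized 4:1 gives 20 × 4/5 = 16 on GWP42003-P and 20 × 1/5 = 4 on placebo. One Case B patient on active treatment would be 1/16 = 6.25% of that arm. This is what one event would weigh if it occurred; it is not an expected frequency. The documents give neither a rate of pre-treatment AEs nor a rate at which they turn serious, so no expected count can be derived.

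**The case against.** A reader might infer that such an event is lost from the serious AE tables altogether. The documents do not support that. Section 13.6.4.2 itself makes the event treatment-emergent through seriousness, so it belongs in the all-causality serious AE table. Sections 12.3 and 12.6 require every SAE to go on an SAE form and into the CRF. Omission would need a flag derived from the start date alone, which the protocol does not specify.

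A reader might also infer that the definition cannot be applied because the AE items A to F in 12.6 hold no date of becoming serious. Those items hold no seriousness field at all, yet serious AEs are to be tabulated, so they cannot be the whole of data capture. SAE forms must be sent within 24 hours of discovery and follow-up forms are dated, which leaves a trail of when the event became serious.

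Nor do the documents show that safety reporting to the sponsor would be missed. Section 12.3 sends all SAEs to pharmacovigilance whatever their causality, and 12.7 recognizes that the sponsor may consider an event related.

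The strongest remaining objection is that 12.5 is silent on a new record for seriousness and does not forbid one. Section 12.1.1 counts deterioration of an existing condition as an AE, and 12.5 also asks the investigator to answer the causality question for every AE and to consider the role of study medication, especially for SAEs. A careful site could therefore enter the deterioration as its own event. That narrows the problem but does not remove it. The one sentence written for pre-treatment events that get worse names severity only, and the sentence before it sets the causality answer. Two sites could follow the protocol and record the same event differently.

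Rarity also counts. Exclusion 6.2.6 removes patients with recent clinically relevant symptoms or significant illness other than epilepsy, and a deterioration serious enough for hospitalization will often raise the severity grade, which brings it under Case A.

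**Conclusion.** The mismatch is real but small. A pre-dose AE that becomes serious on treatment at an unchanged grade is treatment-emergent under 13.6.4.2, yet a literal reading of 12.5 makes it unrelated and so excludes it from the treatment-related AE and serious AE tables. It remains in the data, is reported as an SAE and belongs in the all-causality serious AE table, where the only exposure is to a flag built on onset date.

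This rests on two assumptions: that sites apply 12.5 as written and do not open a separate record on their own initiative, and that 13.6.4.2 stands in Version 2 as in Version 1, which the absence of a listed change supports. The safety analysis is descriptive and no decision rule depends on these tables. The point is minor, but it deserves correction because 12.5 as written can produce a wrong causality entry.

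**What to change.** In 12.5, extend the trigger for a new record from worsening in severity to worsening in severity or seriousness, matching 13.6.4.2. State that the new record takes the date of that change as its start date and carries its own causality answer from the investigator. State also that the sentence treating pre-dose events as unrelated applies only to the pre-dose record.

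The cost is a short edit to 12.5 and the matching line in the CRF completion instructions. Because a new record already has a start date and a causality item, no new data field is needed. The analysis definition in 13.6.4.2 can stay as it is.

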13.6.4.3 Clinical Laboratory Data

Clinical laboratory data at screening and at the end of each 24 day treatment phase and the change from baseline to end of treatment (OLE) will be summarized for the safety analysis set using appropriate summary statistics. Categorical shift tables will also be presented, showing the numbers of patients with values outside the normal range.

13.6.4.4 Columbia-Suicide Severity Rating Scale, Vital Signs, 12-lead Electrocardiogram, Physical Examination and Other Safety Data

The C-SSRS, vital signs, ECG and physical examination data will be summarized at screening, at the end of each 24 day treatment phase and during the OLE treatment period using appropriate summary statistics. Changes in the vital signs from baseline to end of each treatment phase will also be summarized.

